### Aims

The first aim of this study is to highlight possible psychosocial clusters of variables that are specific to the onset and maintenance for each condition (FM, CM, and VU). Specifically, the observation of possible clusters will be made based on variables such as personality traits, defense mechanisms, central sensitization, and childhood traumatic experiences. The hypothesis is that specific psychological factors (clusters of high number of early traumatic events, high levels of central sensitization, and specific traits and defense mechanisms) characterize FM, CM, and VU groups compared to controls reporting other types of CP (e.g., knee arthrosis, rheumatoid arthritis).

A second aim, to give directions for tailored psychological treatments devoted to these conditions, is to explore the association between FM, CM, and VU with depression, anxiety, somatization, quality of life, alexithymia, social support, sexual satisfaction, and functioning. In line with our hypothesis that each of

these conditions has specific areas of psychological sensitivity, this will make it possible to identify specifically for each condition the areas of greatest interest that can be investigated and treated in clinical intervention.

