#### STATYSTICAL PLANNED ANALYSES

The required sample size was estimated a priori for the ANOVA procedure that tested the cluster model sensitivity having 4 groups (migraine, fibromyalgia, vulvodynia, and controls). Using the G\*power program,  $p = 0.05$ , statistical power of 85%, and effect size of 0.35, the calculation yielded a total sample size of  $n = 108$  participants per group (432 as total) The four centers involved in the recruitment of the participants will be the Università di Milano IRCCS Sant'Ambrogio Galeazzi under the head of [name] and Dott. [name], the IRCCS Mondino di Pavia under the head of [name] and [name], The Policlinico San Matteo of Pavia under the head of [name] and Dott. [name], and the Policlinico Umberto I of Sapienza University of Rome under the head of Dott. [name].

ANOVAs and  $\chi^2$  analyses will be carried out to compare groups on sociodemographic characteristics for descriptive reasons and to select possible covariates based on selection bias.

A group of cluster analyses will be performed to classify the samples based on personality traits, defense mechanisms, central sensitization, and childhood traumatic experiences (twenty-two variables corresponding to total scores and thematic subscales of the related measures), aiming to identify different clinical phenotypes within the study samples. A statistical procedure of Two-Step Cluster Analysis will be preferred due to its ability to ensure that one variable does not dominate the cluster solution. Furthermore, it enables the user to identify the importance of each item in the cluster solution. The model fit will be assessed by Schwarz's Bayesian Information Criterion and evaluated by the average silhouette coefficient, an internal validity index representing cluster cohesion and separation quality, ranging between 0 and 1; the closer to 1, the better the model.

Crosstab analyses will be performed to test the association and their strength, and MANOVAs to detect differences in the classification variables based on cluster groups, and Pearson's correlation to explore associations among clusters and other psychological domains. The statistical analyses will be performed using IBM SPSS v. 27.0 and AMOS v.22 (SPSS Inc., Chicago, IL, USA).

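### The planned MANOVAs test cluster differences on the variables that built the clusters, so their p-values are no evidence that clusters exist or differ

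*Combined protocol and SAP*

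**What the plan says.** All of this is in the section on planned statistical analyses of the combined protocol and SAP, unless another section is named.

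- Participants are grouped by Two-Step Cluster Analysis on 22 total and subscale scores covering traits, defences, central sensitisation and early trauma, "aiming to identify different clinical phenotypes within the study samples". The number of clusters is left open.
- The solution is judged by BIC and by the average silhouette, for which the only guidance is "the closer to 1, the better the model". No minimum is set.
- Three analyses follow. The first is "Crosstab analyses will be performed to test the association and their strength", with the two crossed variables not named. The second is "MANOVAs to detect differences in the classification variables based on cluster groups". The third is Pearson's "correlation to explore associations among clusters and other psychological domains".
- The sociodemographic tests carry a stated purpose: to "compare groups on sociodemographic characteristics for descriptive reasons" and to choose covariates. The MANOVA has no descriptive label, and no hold-out sample or adjustment for selection is planned.
- Two-Step is preferred partly because "it enables the user to identify the importance of each item in the cluster solution".
- The Aims section expects psychological factors that "characterize FM, CM, and VU groups compared to controls reporting other types of CP".

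**The concern.** A MANOVA p-value is calibrated for group labels fixed independently of the outcomes. Here an algorithm draws the labels so that the groups lie far apart on those outcomes. A small p-value then shows only that the algorithm did its job; it would appear in a population with no subgroups at all.

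The study's purpose is to describe phenotypes and to guide tailored psychological treatment. A results table in which every cluster contrast is extremely significant would read as confirmation that the phenotypes are real. The p-values cannot carry that weight.

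A related problem affects the step that does look outside the clustering set. Cluster membership is nominal. With three or more clusters, a Pearson coefficient computed on the cluster number depends on which cluster happens to be called 1, 2 or 3.

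**Working it through.** **Inputs.** From the plan: 22 clustering variables, alpha 0.05, N = 4 × 108 = 432. The plan gives no figure for the MANOVA, so there is none to reproduce. Assumed: the number of clusters k, the correlations among inputs, and block sizes of 5, 5, 6 and 6, because the 22 variables are not listed.

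**Step 1, by hand for k = 2.** With p = 22 variables, F = [(1 − Λ)/Λ] × [(N − p − 1)/p] on 22 and 409 df, where Λ is Wilks' lambda.

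- Labels unrelated to the data: expected Λ = 409/431 = 0.949, so F = (0.051/0.949) × (409/22) ≈ 1.0. The 5% critical value is 1.57.
- One normal population cut at its mean along any single direction: the between-group share of variance in that direction is 2/π = 0.637, so Λ is at most about 0.363. Then F = (0.637/0.363) × 18.59 ≈ 32.6, with p about 6e-76.
- Simulated k-means at a common correlation of 0.3: median Λ = 0.339, so F = (0.661/0.339) × 18.59 ≈ 36.2.

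The arithmetic and the simulation agree: splitting a single population is enough to produce an extreme p-value.

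**Step 2, simulation with no true clusters.** Inputs were independent normals, or one general plus four block factors with between/within-block r of 0.1/0.3, 0.2/0.4 and 0.3/0.5. K-means used k = 2, 3 and 4, with 200 runs per setting: 3 × 4 × 200 = 2,400.

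| Test | k-means | Two-Step-like emulation, sets keeping ≥ 2 clusters |
|---|---|---|
| MANOVA on the clustering variables, p < 0.001 | 2,400/2,400 (largest p about 8e-70) | 208/208 (largest p about 6e-28) |
| Same, labels permuted, p < 0.05 | 102/2,400 (4.3%) | 7/208 (3.4%) |
| ANOVA of an unrelated outside variable, p < 0.05 | 122/2,400 (5.1%) | 9/208 (4.3%) |
| Crosstab with randomly assigned diagnosis, p < 0.05 | 131/2,400 (5.5%) | 13/208 (6.3%; exact 95% interval 3.4% to 10.5%) |

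The permuted rows show that the MANOVA itself is sound and that reusing the variables breaks it. A second simulation used k-means and Ward clustering, N of 108 or 432, and common correlations of 0, 0.3 and 0.5. It rejected at 0.05 in all 36 × 300 = 10,800 data sets.

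**Step 3, would BIC stop it?** The emulation used log-likelihood distance and a BIC-chosen number of clusters; it is not SPSS. It kept two or more clusters in 0 of 60 independent-normal sets, 28 of 60 with six skewed inputs, and 60 of 60 at each of the three correlation levels: 28 + 180 = 208. In a separate batch with correlated inputs, the mean silhouette was 0.09 to 0.15.

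**Step 4, Pearson on the label.** Take three equal clusters with outcome means 0, 1 and 2. Numbered in that order, the covariance of label and mean is 2/3. Swap the last two numbers and it is 1/3, so |r| halves with no change in the data. In the correlated k-means runs, the outside variable shared the general factor. Renumbering alone moved mean |r| from 0.06–0.16 to 0.19–0.44 (k = 3) and from 0.02–0.04 to 0.20–0.45 (k = 4). Significance at 0.05 depended on the numbering in 242 of 600 runs (k = 3) and 571 of 600 (k = 4). ANOVA is unaffected by numbering.

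**Step 5, limits of the replacement tests.** These used no discrete clusters, r of 0.2/0.4, k-means with k = 2, 3 and 4, and 100 runs each. Shifting the three pain groups on one continuous factor made the crosstab reject in 14% to 26% of runs (0.25 SD) and 61% to 77% (0.5 SD). In no-cluster runs with correlated inputs, an outside variable sharing that factor was significant by ANOVA in 94.5% to 100%. Both tests detect association, not discreteness.

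**The case against.** The plan never says that the MANOVA will show clusters to be real; it assigns that job to BIC and the silhouette. On this reading the MANOVA only profiles the clusters. That is a fair account of what may be intended, and it limits the consequence, but the stated purpose is to detect differences and nothing marks the result as descriptive. If description is meant, the p-values add nothing.

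The silhouette would also give some warning: values of 0.09 to 0.15 on a 0-to-1 scale look poor. This stands in part. Without a minimum value, however, the plan does not say that such a solution would be abandoned.

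The plural could mean one MANOVA per domain. That does not help: block-level MANOVAs under the same no-cluster conditions still gave p < 0.05 in 99.8% to 100% of tests.

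The Pearson wording could mean correlating scores within clusters. In addition, the emulation chose two clusters in 188 of the 208 kept sets, and with two clusters a correlation with the label is valid. The point therefore applies to the literal reading and only with three or more clusters.

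Finally, the retention rates rest on assumed inputs and are not SPSS output. If some totals are exact sums of included subscales, the 22-variable MANOVA could not be computed as modelled. Both caveats stand. The circularity needs only that two or more clusters be kept and tested on their own inputs.

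**Conclusion.** The concern holds, with high confidence, and the plan should be changed. Given two or more retained clusters, the planned omnibus p-value is near certain to be extreme whether or not subgroups exist, so it is not evidence that clusters exist or differ. Single-variable results still rank stronger and weaker contributors, but only as a description of the partition. How often a spurious solution would be kept is less certain: 0 of 60 to 60 of 60 in the emulation, depending on the assumed inputs.

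The damage is confined to the MANOVA and, with three or more clusters, to Pearson correlation with the label. The cluster-by-diagnosis association remains valid as a test of association.

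**What to change.** 1. Report the clustering variables by cluster as means, SDs and effect sizes, or use the Two-Step importance measure the plan already cites. Drop the MANOVA p-values and any significance claim based on them. State that these effect sizes describe the partition and do not estimate population differences.
2. Specify the crosstab as cluster by diagnosis, read as a test of association only.
3. Compare other psychological domains across clusters by one-way ANOVA, or another test that treats cluster as nominal. With three or more clusters, this replaces Pearson correlation with the label.
4. State that neither result proves discrete phenotypes.
5. For the optional questionnaires, give the number completing each and say that the subset is self-selected. The Mental Pain Questionnaire is asked of everyone and can serve on the full sample if it is not among the 22.

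The cost is wording, with no new data. The results table will look less striking, and there will be no formal test on the clustering variables. ANOVA will need follow-up contrasts to say which clusters differ, and comparisons on the optional measures will rest on a smaller, self-selected sample.

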### Abstract

Chronic pain (CP) is a substantial healthcare challenge with considerable economic costs. Recently, the term of Nociplastic Pain (NP) has been advanced as a third descriptor of mechanisms related to CP. NP describes conditions that arise from altered nociception despite no clear evidence of actual or threatened tissue damage. It is a new way of describing somatoform painful conditions, originating from altered central-nervous pathways (e.g., central sensitization) and with the important involvement of clinical psychological factors. Among nociplastic chronic syndromes have been included fibromyalgia (FM), chronic migraine (CM) and vulvodynia (VU). These chronic pain disorders have been usually studied separately, although the high comorbidity rates. Many studies evidenced the role of psychosocial variables in the onset and maintenance of the burden related to these conditions. Among them, personality traits, defense mechanisms, central sensitization, and childhood traumatic experiences may play a pivotal role in the onset of the NP. The first aim of this study is to highlight possible psychosocial clusters of variables that are specific for each condition (FM, CM, and VU). A second aim, to improve the tailored psychological treatment devoted to these conditions, is to explore the association between FM, CM, and VU with depression, anxiety, somatization, quality of life, alexithymia, social support, sexual satisfaction, and functioning. This will make it possible to identify specifically for each condition the areas of greatest interest that can be investigated and treated in clinical intervention. To identify specific descriptors, NP conditions will be compared with a control group of subjects reporting other types of CP (e.g., knee arthrosis, rheumatoid arthritis). The study involves the collection of data from a self-administered questionnaire in several Italian centers specializing in the above-mentioned clinical conditions under the guidance of the research team of the Department of Dynamic and Clinical Psychology and Health Studies, PI [name].

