In addition to this, the study of psychosocial factors associated with the experience of such pathologies or possible emerging clusters such as depression, anxiety, somatization, quality of life, alexithymia, social support, sexual satisfaction, and functioning. This will make it possible to identify specifically for each condition the areas of greatest interest that can be investigated and treated in clinical intervention tailored to the person.

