## MEASURES

The study involves the administration of a protocol of self-report questionnaires consisting of two parts: the main (about 25 minutes for the administration) and the optional one (additional 20 minutes). This decision stems from the realization of the length of the protocol, to increase the collection of data in pursuit of the main objective of the study (cluster analysis).

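### The second aim is set by diagnosis, but the plan states no analysis of its domains by diagnosis; the only stated method relates them to clusters

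*Combined protocol and SAP*

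**What the plan says.** The Aims section sets the second aim by diagnosis: to "explore the association between FM, CM, and VU with depression, anxiety, somatization, quality of life, alexithymia, social support, sexual satisfaction, and functioning". The hypothesis is that each of "these conditions has specific areas of psychological sensitivity", and the purpose is to "identify specifically for each condition the areas of greatest interest" for clinical intervention. The Abstract says in general terms that "NP conditions will be compared with a control group of subjects reporting other types of CP". The Aims section mentions controls only under the first aim.

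The rationale on psychological factors is wider. It speaks of studying "psychosocial factors associated with the experience of such pathologies or possible emerging clusters".

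The statistical planned analyses section is the only place where methods are given. Its ANOVAs and chi-square tests are to "compare groups on sociodemographic characteristics for descriptive reasons and to select possible covariates based on selection bias". The cluster analysis uses the first-aim variables (personality traits, defence mechanisms, central sensitization, childhood trauma). The crosstabs name no variables. The MANOVAs compare the classification variables between clusters. The last method is Pearson's "correlation to explore associations among clusters and other psychological domains".

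The instruments for the second-aim domains are in the optional part of the questionnaire.

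**The concern.** A reader who wants to know whether, say, alexithymia or quality of life differs between FM, CM and VU will find no stated analysis that answers it. The one stated method uses a different grouping variable. Followed as written, the plan would yield statements about clusters, while the aim promises statements about conditions that are meant to guide tailored treatment. The model, the contrasts and the role of the controls would be left to be settled at the analysis stage.

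There is a second, conditional problem. If clusters enter the correlation as a numbered label with three or more unordered categories, Pearson's r depends on which cluster is called 1, 2 or 3. The plan does not say how clusters are coded.

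**Working it through.** **1. Match each stated method to its outcome and grouping variable.**

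| Stated method | Outcome | Grouping variable | Second-aim domain by diagnosis? |
|---|---|---|---|
| ANOVA, chi-square | sociodemographic characteristics | groups | no |
| Two-Step clustering | first-aim variables | none (forms the clusters) | no |
| Crosstabs | not named | not named | none stated |
| MANOVA | classification variables | cluster | no |
| Pearson's correlation | other psychological domains (not defined) | cluster | no |
| ANOVA in the sample-size paragraph | not named; described as testing the cluster model | four diagnosis groups | none stated |

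The Aims section lists eight domains: depression, anxiety, somatization, quality of life, alexithymia, social support, sexual satisfaction, functioning. The number with a stated diagnosis-group analysis is 0 of 8.

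**2. The plan's own sample-size figure.** The stated inputs are four groups, alpha 0.05, power 85% and effect size 0.35. The metric is not stated; it is taken here as Cohen's f. For a one-way omnibus ANOVA the noncentrality is N × f². With N = 108 in total (27 per group) it is 108 × 0.35² = 13.23 and power is 0.863. With N = 104 power is 0.848. So these inputs give 108 in total, whereas the plan states 108 per group, 432 in total. The mismatch does not affect the present point, but it matters for which n the precision below rests on. The plan states 432, so 108 per group is used.

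**3. Precision of the missing estimate.** Half-width of the 95% interval in SD units = t(0.975, df) × √(1/n₁ + 1/n₂), with pooled variance, no covariates and no multiplicity correction.

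- 108 per group, df = 432 − 4 = 428: 1.966 × √(2/108) = 0.267.
- 54 per group (50% completion, assumed), df = 216 − 4 = 212: 1.971 × √(2/54) = 0.379.
- Women only, 108 with VU against 54 women in each other group (half women, assumed), df = 270 − 4 = 266: 1.969 × √(1/108 + 1/54) = 0.328.
- The same at 50% completion, 54 against 27, df = 135 − 4 = 131: 1.978 × √(1/54 + 1/27) = 0.466.
- If recruitment were only 27 per group, df = 104: 1.983 × √(2/27) = 0.54.

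**4. Pearson's r with a cluster label (all inputs assumed).** Take three equal clusters with domain means 0, 0.4 and 0.8 and within-cluster SD 1.

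- Between-cluster variance = (0.4² + 0 + 0.4²)/3 = 0.107; total variance 1.107; eta-squared = 0.107/1.107 = 0.096.
- Labels 1, 2, 3 in order of the means: covariance = (0.4 + 0 + 0.4)/3 = 0.267; r = 0.267/(√(2/3) × √1.107) = 0.31.
- Reversing the labels gives r = −0.31, and other orders fall between. Eta-squared stays at 0.096.

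With two clusters eta-squared equals r², so a nominal factor loses nothing in strength of association.

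**The case against.** Several things can fairly be said for the plan.

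- **Clusters are a stated framing.** The rationale offers pathologies or clusters as alternatives, so a reader might infer that relating the domains to clusters departs from the study's intent. It does not, and that analysis should stay. But the Aims section and the Abstract set the second aim by condition, and that part has no stated analysis.
- **Some group model may be intended.** Selecting covariates has no evident use in clustering, crosstabs or Pearson's r, and the sample-size paragraph refers to an ANOVA on the four diagnosis groups. So a reader should not infer that a diagnosis comparison has been ruled out. It is unstated: neither place names a second-aim outcome.
- **Clustering might be run within each diagnosis.** The plan speaks of several cluster analyses. On that reading, cluster-by-domain associations would be specific to each condition, but there would still be no estimate between conditions.
- **Most scores are tied to an instrument.** A reader might infer that every second-aim score is left to be chosen after the data are seen. The list of optional questionnaires does not support that. It gives BSI-18 scales for depression, anxiety and somatization, two SF-12 summary measures for quality of life, and one instrument each for alexithymia, social support and sexual satisfaction. What stays open is total or subscale for some instruments, the meaning of functioning, and the contrasts.
- **Pearson's r is not always wrong.** It is valid with two clusters, 0/1 indicators or continuous scores.
- **The aim is secondary.** The Measures section calls cluster analysis the main objective. That justifies an exploratory label, but the second aim carries its own hypothesis and needs a stated analysis.

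**Conclusion.** The point holds and should be fixed before the data are analysed. The plan states a diagnosis-group analysis for 0 of the 8 second-aim domains, and the method it does state answers a different question. This rests on reading the methods as written. It does not depend on any assumed figure.

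The Pearson problem is conditional on cluster membership being a label with three or more unordered categories. The example of r moving between −0.31 and +0.31 rests on assumed means.

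Whether controls belong in the second aim is unsettled: the Abstract implies that they do, while the Aims section names them only under the first aim. The plan needs to say which.

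The missing estimate is obtainable from data already planned: about ±0.27 SD per pairwise difference at the stated 108 per group with full completion, and ±0.38 SD at an assumed 50% completion.

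**What to change.** In the statistical planned analyses section:

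1. Add, labelled exploratory, an ANOVA or ANCOVA by diagnosis group for each second-aim score, reporting group mean differences with 95% confidence intervals.
   - State whether controls are included.
   - State which total or subscale score is used where an instrument offers several, and what functioning means.
   - Handle sex explicitly, because VU occurs only in women. One way is a women-only analysis of contrasts with VU, as the main analysis or as a sensitivity analysis.
   - Analyse the FSFI and the IIEF within sex.
2. For the cluster-by-domain analysis, enter cluster membership as a nominal factor (ANOVA with eta-squared), and keep Pearson's r for pairs of continuous scores.
3. Because the second-aim scales are optional, report the number completing each scale by group.

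The cost is a short added text and somewhat more analysis, with no new instruments or visits. Precision falls where completion is low and in single-sex contrasts. For VU against a group in which half are women (assumed), the interval is about ±0.33 SD with full completion and ±0.47 SD at 50% completion.

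### Pearson's correlation is the only method named for relating clusters to the other psychological domains, and the plan does not say how cluster membership enters it; used as a numeric code with three or more clusters, r would depend on arbitrary numbering.

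*Combined protocol and SAP*

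**What the plan says.** Everything on this point is in the section STATYSTICAL PLANNED ANALYSES of the combined protocol and SAP.

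- **Clustering method.** "A statistical procedure of Two-Step Cluster Analysis will be preferred", "aiming to identify different clinical phenotypes within the study samples". No order or severity ranking of the phenotypes is stated.
- **Number of clusters.** Not fixed in advance. Fit is judged by Schwarz's "Bayesian Information Criterion and evaluated by the average silhouette coefficient".
- **Analyses after clustering.** One sentence names three. The first is crosstabs: "Crosstab analyses will be performed to test the association and their strength". The second is "MANOVAs to detect differences in the classification variables based on cluster groups". The third is Pearson's "correlation to explore associations among clusters and other psychological domains".

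The domains can be read from the second aim (section Aims), which concerns associations of the three diagnoses "with depression, anxiety, somatization, quality of life, alexithymia, social support, sexual satisfaction, and functioning". Most of these scores come from the questionnaires listed as optional. The section on psychological factors in nociplastic pain adds that such factors may be studied in relation to the diagnoses or to any clusters that emerge.

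**The concern.** Two-Step clustering assigns each participant a label. The labels 1, 2, 3 name types; they are not amounts. Pearson's r treats whatever it is given as a quantity with equal steps, so a correlation with the label assumes that cluster 2 lies midway between clusters 1 and 3. Nothing in the plan supports that, and renumbering the same clusters would change the answer.

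No other stated analysis covers the comparison. The MANOVAs are limited to the variables that formed the clusters. Crosstabs would reach a continuous domain score only if it were first cut into categories, which the plan does not mention. The ANOVAs in the same section are for sociodemographic comparisons. The ANOVA in the sample-size paragraph has the four diagnostic groups as its groups and names no domain score.

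At stake is whether one phenotype has more depression, or worse quality of life, than another. A real difference could be reported as no association, or with a sign that carries no meaning.

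**Working it through.** The plan states no figure for this correlation, so there is none to reproduce. The check asks how far r can move when only the cluster numbers change.

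**Inputs.** From the plan: an unordered cluster label, a continuous domain score, and an unspecified number of clusters. Assumed, because the documents give none: cluster means, cluster shares p, and a within-cluster SD of 1.

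**Formulas.** Let c be the code and m the domain mean of a cluster, with C and M their averages weighted by p.

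- Between-cluster variance B = Σ p(m − M)²; total variance of the score = B + 1.
- Eta-squared = B / (B + 1). It does not involve c.
- r = Σ p(c − C)(m − M) / √[Var(c) × (B + 1)].

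**Case 1: three equal clusters, means 0, 0, 1.**

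- M = 1/3, so B = (1/9 + 1/9 + 4/9)/3 = 0.222. Eta-squared = 0.222/1.222 = 0.182.
- Var(c) for codes 1, 2, 3 is 2/3, so the denominator of r is √(0.667 × 1.222) = 0.903.
- Distinct cluster coded 3: covariance = [(−1)(−1/3) + 0 + (1)(2/3)]/3 = 0.333, so r = 0.333/0.903 = +0.37.
- Distinct cluster coded 1: by symmetry r = −0.37.
- Distinct cluster coded 2: covariance = [(−1)(−1/3) + 0 + (1)(−1/3)]/3 = 0, so r = 0. This is 2 of the 6 numberings, or one third.

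**Case 2: three equal clusters, means 0, 0.5, 1.**

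- B = (0.25 + 0 + 0.25)/3 = 0.167. Eta-squared = 0.167/1.167 = 0.143, and eta = 0.378.
- Over the six numberings r is +0.378, +0.189 (twice), −0.189 (twice) and −0.378.
- With cluster shares of 50%, 30% and 20% and the same means, eta is 0.364, while r runs from −0.364 to +0.364, with |r| as low as 0.113.

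**Case 3: four equal clusters, means 0, 0.5, 1, 1.5.**

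- B = 2 × (0.5625 + 0.0625)/4 = 0.3125. Eta-squared = 0.3125/1.3125 = 0.238.
- Codes in order 1, 2, 3, 4: covariance 0.625, so r = 0.625/√(1.25 × 1.3125) = +0.488. Reversed codes give −0.488.
- Codes 2, 4, 1, 3: (0.375 − 0.375 − 0.375 + 0.375)/4 = 0, so r = 0.

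**Case 4: two equal clusters, means 0, 0.8.**

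- B = 0.16. Eta-squared = 0.16/1.16 = 0.138, and eta = 0.371.
- r is +0.371 or −0.371. Its size equals eta, and only the sign depends on coding.

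With two clusters, then, the size of r is sound. With three or more, size and sign both move while eta-squared stays fixed.

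**The case against.** The strongest objection is that the plan never says the label is the variable being correlated. Elsewhere the protocol uses the word clusters for sets of psychological variables, for example in Aims, and the MANOVA clause speaks of cluster groups while the correlation clause says only clusters. The sentence could therefore mean continuous clustering scores correlated with continuous domain scores, which is a proper use of Pearson's r. It could also mean correlations computed within each cluster, or indicator variables. This stands as an ambiguity: a reader might infer that a correlation with the raw label is definitely planned, and the text does not go that far. It does not remove the point. The same section uses clusters for classified participants. On the variable-set or within-cluster readings, no stated analysis would show whether clusters differ on a domain.

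Three further objections stand.

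- The defect in size needs three or more clusters, and the plan leaves the number open.
- The step is labelled exploratory. The first aim is served by clustering, crosstabs and MANOVA, and the second aim is framed around diagnoses.
- The cluster means and sizes used above are assumptions, and some were chosen to show cancellation. They show what can happen, not what is expected here.

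**Conclusion.** The point holds conditionally. The plan leaves undefined how clusters enter the correlation and names no alternative for this comparison. If the label is used as a number and there are three or more clusters, r is not interpretable. Under the assumed means, an association with eta-squared between 0.14 and 0.24 can appear with either sign and a much reduced size, and in two of the examples as exactly zero. With two clusters only the sign is arbitrary.

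A reader might go further and infer that the reported associations will be arbitrary, or that the main result of the study is at risk. The documents do not support either inference: the number of clusters and the coding are unknown, and the clustering itself does not use this correlation. This is a should-fix item.

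**What to change.** Replace the correlation clause with wording to this effect: each domain score will be compared across clusters with cluster membership as a categorical factor (ANOVA, or MANOVA for related scales), reporting eta-squared and pairwise cluster differences with 95% CIs; Pearson's correlation will be used only between pairs of continuous scores. If correlations between clustering scores and domain scores, or correlations within clusters, are also wanted, name the pairs and state that they answer a different question.

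Nothing is lost if two clusters emerge, since eta then equals the absolute value of r. Adjustment for diagnosis or covariates is an optional secondary model and not part of this correction. It would change the quantity estimated to a cluster difference within diagnosis, and the plan has no prespecified covariate list, because covariates are to be chosen from the group comparisons.

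The cost is one sentence, settled before analysis, with the same data and the same software.
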